5.4 DLQI Questionnaire (PsA)

- Descriptive statistics of the DLQI score at baseline, at each visit, and at the last observation.
- Descriptive statistics of the change in DLQI score between baseline and each visit, and between baseline and the last observation.
- Descriptive statistics of each DLQI scale at baseline, at each visit and at the last observation.
- Descriptive statistics of the change in each DLQI scale between baseline and each visit, and between baseline and the last observation.
- Frequency distribution of the DLQI category at baseline, at each visit, and at the last observation.
- Frequency distribution of the regrouped DLQI category at baseline, at each visit, and at the last observation.
- Frequency distribution of the regrouped DLQI category at each visit, and at the last observation, broken down by the regrouped DLQI category at baseline.

5.5 HAQ-DI (PsA)

- Descriptive statistics of the HAQ-DI score at baseline, at each visit, and at the last observation.
- Descriptive statistics of the change in the HAQ-DI score between baseline and each visit, and between baseline and the last observation.

5.6 BASDAI (AS)

- Descriptive statistics of the BASDAI total score at baseline, at each visit, and at the last observation.
- Descriptive statistics of the change in BASDAI total score between baseline and each visit, and between baseline and the last observation.
- Frequency distribution of the BASDAI total score category (axial disease) at baseline, at each visit, and at the last observation.
- Frequency distribution of the BASDAI total score category (axial disease) at each visit and at the last observation, broken down by the BASDAI total score (axial disease) at baseline.

5.7 HAQ-S (AS)

- Descriptive statistics of the HAQ-S score at baseline, at each visit, and at the last observation.
- Descriptive statistics of the change in the HAQ-S score between baseline and each visit, and between baseline and the last observation.
- Frequency distribution of the possibility of performing daily activities at baseline, at each visit, and at the last observation.
- Frequency distribution of the possibility of performing daily activities at each visit and at the last observation, broken down by the possibility of performing daily activities at baseline.
- Descriptive statistics of the HAQ-S additional items (pain, general health, stiffness) score at baseline, at each visit and at the last observation.
- Descriptive statistics of the change in the HAQ-S additional items between baseline and each visit, and between baseline and the last observation.

5.8 Physician and Patient Assessments of Disease Activity and Patient Assessment of Pain

- Descriptive statistics at baseline, at each visit and at the last observation.
- Descriptive statistics of the change between baseline and visit, and between baseline and the last observation.

5.9 Acute Phase Reactants

- Descriptive statistics at baseline, at each visit and at the last observation.
- Descriptive statistics of the change between baseline and each visit, and between baseline and the last observation.

5.10 Relation Between Work Status and Clinical Evaluations

For DAS28 score, BSA, DLQI score, HAQ-DI score, BASDAI total score, HAQ-S (total score and scores for pain during the past week, general health, and stiffness), physician and patient assessments of disease activity, and patient assessment of pain:

- For baseline, Month 18, and the last attended visit:
 - Descriptive statistics broken down by work status (Q1 of the WPAI).
 - Evaluation of the effect of work status (and indication) by means of analysis of variance.
- For the change between baseline and Month 18, and between baseline and the last attended visit, descriptive statistics broken down by work status (Q1 of the WPAI) at baseline.

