3.2. Psoriatic arthritis

Psoriatic Arthritis (PsA) is an inflammatory arthropathy that occurs in up to one third of patients with psoriasis and is usually diagnosed years after the appearance of psoriatic skin disease, but may also precede it.

Synovitis of peripheral joints is a major feature of PsA, and joint affection can be monoarthritic, oligoarthritic, or polyarthritic. More than half of patients with PsA exhibit progressive, erosive arthritis that often is associated with functional impairment. PsA may also affect the axial skeleton: the spine can be involved in any part, most often at the lumbosacral transition and the neck.

PsA can develop at any time, but for most people it appears between the ages of 30 and 50, and it affects men and women equally. The overall prevalence of PsA is approximately 0.1% (22, 23).

Work disability in PsA and its costs

There is a dearth of published pharmacoeconomic studies in PsA, despite increasing evidence that affected patients can have significant radiographic joint damage, functional impairment, reduced quality of life (QoL) and long-term work disability. Among patients treated with anti-TNF agents and registered in the British Society for Rheumatology Biologic Register, work disability rates were 39% for PsA patients, 41% for AS patients and 49% for those with RA (24). Somewhat lower rates were reported for Norwegian PsA

patients on either conventional or biologic DMARD (disease modifying anti-rheumatic drugs) therapy: work disabled were 32.7% of females and 17.4% of males (25).

Treatment of PsA

The treatment of PsA is directed at controlling the inflammatory process. Although there is no clear correlation between the skin and joint inflammation in every patient, the skin and joint aspects of the disease need to be treated simultaneously. Initial treatment consists of NSAIDs for joint disease and topical or systemic therapy for the skin. More severe disease is likely to require treatment with DMARDs, such as MTX, and intra articular steroids. Among second-line treatments used in RA and evaluated in patients with PsA are sulfasalazine, MTX, leflunomide, gold, antimalarials, cyclosporine, and azathioprine (26).

Anti-TNF agents are highly effective in treating the signs and symptoms of PsA, including dactylitis and enthesitis, and they also suppress structural joint damage and treat skin psoriasis (27).

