10.3.2 Statistical Analysis

The study is essentially descriptive. The numerical variables will be analyzed applying descriptive statistics (mean, 95% confidence interval on the mean, standard deviation, minimum, 1st quartile, median, 3rd quartile, maximum, number of observations).

Quantitative variables will be described by means of frequencies and percentages for the

different categories. For the variables recorded for both AS and PsA patients the descriptions will be given for all patients as well as separately for each subgroup.

The analysis of the evolution of the work productivity data, the health-related quality of life scores, and the disease activity measures and clinical evaluations will be based upon data collected during time windows around the foreseen routine study visits.

The relationship between disease activity and work status and between clinical evaluations and work status will be evaluated by comparing the onset data for patients currently employed and patients not employed at the baseline visit, and by comparing the data from the 18 month time window for patients currently employed and patients not employed at the corresponding visit.

The relationship between disease activity and work productivity and between clinical evaluations and work productivity will be evaluated on the basis of the correlations with the TWPI for the baseline data.

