1. METHODOLOGY

The purpose of this statistical analysis plan is to provide detailed information on the statistical analysis of the data of study P13-990. The plan is based on the final protocol, incorporating administrative change 1, dated 17 December 2015.

1.1 *Introduction*

Ankylosing spondylitis (AS) and psoriatic arthritis (PsA) are both associated with often debilitating clinical symptoms, reduced functional impairment and significant impact on quality of life. As a consequence both diseases imply a significant economic burden, arising from both the direct costs of medical and disability. Health economics data becomes increasingly important to justify the costs of medicines.

Very limited data are available about the employment status and the work productivity of patients with AS and PsA in Belgium. The same is true for the impact of adalimumab treatment on employment status and work productivity.

The aim of this study is to analyse the employment status and work productivity of patients with AS and PsA before and after the start of adalimumab and to look at the relationship between employment status, work productivity, disease activity and clinical evaluations.

1.2 *Study Objectives and Endpoints*

1.2.1 *Study Objectives*

The main objective of the study is to observe in daily practice the evolution of work productivity over 18 months in AS and PsA patients after the start of adalimumab treatment.

The following questions were addressed:

- What is the employment status of AS and PsA patients with active disease before initiation of adalimumab?
- In the patients who work at baseline, what is their work productivity?
- Does adalimumab therapy enable people with AS and PsA to return to work or work more productively?

The secondary objectives are to:

- Investigate if there is a difference in evolution of employment status and work productivity after initiation of adalimumab treatment between AS and PsA patients throughout the study
- Investigate the relationship between disease activity and employment situation and the relationship between clinical evaluations and employment situation at baseline and after 18 months
- Investigate possible correlations between disease activity and work productivity and between clinical evaluations and work productivity

1.2.2 *Study Endpoints*

The primary endpoints is Total Work Productivity Impairment (TWPI) due to AS/PsA:

18 months versus baseline in all patients, measured by the WPAI-SHP questionnaire.

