1.5 Study Data Considered for the Analysis

The following data are used for the analysis:

Data only collected at screening (baseline)

- Date of inclusion (screening) and date informed consent form was signed
- Demographic data
 - Year of birth
 - Gender
 - Ethnic origin (Caucasian, Hispanic, Black, Asian, Other).
- Indication for adalimumab therapy (ankylosing spondylitis, psoriatic arthritis) and year of diagnosis.
- Extra-articular disease manifestations: None or
 - Psoriasis
 - Inflammatory bowel disease
 - Uveitis
For each manifestation: Yes/no and (currently active, currently inactive)
- Smoking status (never smoked, ex-smoker, smoker, unknown)
- Other medical history: None or
 - Cardiovascular diseases
 - Cardiovascular risk factors
 - Diabetes
 - Renal disease
 - Hepatic disease
 - Lung disease
 - Mental disorders
 - Other and specification
- Medication history
 - Analgesics
 - NSAIDs

- DMARDs
- Steroids
- Biologic therapy.
- Education background (highest level achieved): None, primary school, secondary school, higher education (non-university), university.
- Start date adalimumab therapy.

Data collected at each visit

- Date of visit
- Employment situation (to be answered at baseline, and at each follow-up visit in case of any change since the last visit):
 - Current employment status:
 - Housewife/houseman, due to As/PsA (yes, no)
 - Unemployed, due to As/PsA (yes, no)
 - Retired, due to As/PsA (yes, no)
 - Part-time employed: Percentage, due to As/PsA (yes, no)
 - Full-time employed
 - Student.
 - Current job content:
 - Professional or technical
 - Administrative or managerial
 - Sales
 - Service tasks
 - Agricultural
 - Production/manufacturing, transport equipment operator, laborer
 - Armed forces
 - Other and specification.
 - Current occupational situation:
 - Employee
 - Independent
 - Public/civil servant
 - Volunteer
 - Other
- Disease activity measures and clinical evaluations:
 - Only PsA
 - Body Surface Area (BSA) affected (no psoriatic lesions, <3%, 3-10%, 11-20%, >20%).
 - DAS28 score.
 - Only AS
 - BASDAI
 - Consists of 6 items assessed on ordinal scales. Higher scores indicate higher severity. The scores for Items 1 to 5 are integers between 0 and 10. The scores for Item 6 is a continuous assessment between 0 and 10.
 - The total score is calculated as:
[(Item 1+Item 2+Item 3+Item 4)+(Item 5+Item 6)/2]/5

PsA and AS

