1.7 Statistical Methodology

The analysis will consist of data descriptions and statistical hypothesis testing. Throughout this document, the following terminology is used for indicating the type of descriptive analysis to be performed:

- ‘Descriptive statistics’ is used to indicate the description to be provided for quantitative variables, and includes the mean, standard deviation, 95% confidence interval (CI) on the mean, minimum, 1st quartile, median, 3rd quartile, maximum,

- number of available observations, and number of missing observations.
- ‘Frequency distribution’ is used to indicate the description to be provided for categorical variables and consists of numbers and percentages for each of the scores or categories.

For the variables recorded for both AS and PsA patients the descriptions will be given for all patients as well as separately for each subgroup.

The relationship between TWPI and disease activity at baseline and between TWPI and clinical evaluations at baseline will be evaluated by means of the Spearman rank correlation coefficient.

The relationship between work status and disease activity and between work status and clinical evaluations will be evaluated by means of analysis of variance, controlled for indication, if applicable.

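### SAP 5.10 tests the effect of work status with indication as the only adjuster, so most scores are compared with no adjustment although age, sex, education and year of diagnosis are collected

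*SAP*

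**What the plan says.** One secondary objective in SAP 1.2.1 is to "Investigate the relationship between disease activity and employment situation and the relationship between clinical evaluations and employment situation at baseline and after 18 months". SAP 5.10 is the section that compares the scores by work status to serve it. For each listed score it gives descriptive statistics by the answer to WPAI question 1, and then "Evaluation of the effect of work status (and indication) by means of analysis of variance". This is done at baseline, Month 18 and the last attended visit. SAP 1.7 describes the same model as "analysis of variance, controlled for indication, if applicable". Neither section names another covariate, a stratified analysis or a sensitivity model.

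SAP 1.5 shows what is available at baseline: year of birth, gender, highest education in five levels, and "Indication for adalimumab therapy (ankylosing spondylitis, psoriatic arthritis) and year of diagnosis". SAP 1.6 derives age but not disease duration. SAP 3.1 and 3.3 describe age, gender and education overall and by indication, not by work status. Year of diagnosis is not summarised anywhere in SAP section 3. The only baseline characteristic broken down by employment status is extra-articular manifestations (SAP 3.2).

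On the nature of the analysis, Protocol 10.3.2 states: "The study is essentially descriptive". SAP 1.7 goes further: "The analysis will consist of data descriptions and statistical hypothesis testing".

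**The concern.** Patients who are not working may differ from those who are in sex, age, schooling and time since diagnosis. Where such a factor is also related to the clinical score, the unadjusted difference combines the relation of interest with the difference in patient mix. Protocol 3.2 itself supplies one such link, a higher rate of work disability in women than in men with PsA. In addition, a No to WPAI question 1 can pool homemakers, unemployed, retired patients and students, so the non-working group is partly defined by age and social role.

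At stake is how the second secondary objective is read. A reported, tested effect of work status on disease activity invites the reader to credit the whole difference to disease. The plan gives no adjusted estimate, and no table of age, sex or education by work status, from which to judge that.

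**Working it through.** **Plan's own figure.** The documents give no figure for the 5.10 analysis. The precision table in SAP 1.4 concerns the change in TWPI. It reproduces as mean ± t(0.975; 99) × SD/√100 (for example −10 ± 1.984 × 2.38 = [−14.7; −5.3]) and is not affected by this point.

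**Which comparisons are adjusted.**

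| Measure in SAP 5.10 | Recorded in | Can indication enter? |
|---|---|---|
| DAS28, BSA, DLQI, HAQ-DI | PsA only | No |
| BASDAI; HAQ-S total, pain, general health, stiffness | AS only | No |
| Physician and patient disease activity, patient pain (VAS) | Both | Yes |

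**Difference in sex mix.** Inputs from Protocol 3.2: 0.327 of women and 0.174 of men work disabled. Assumptions: equal numbers of men and women, and the work-disabled split standing in for the WPAI question 1 split.

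- Odds ratio = (0.327/0.673)/(0.174/0.826) = 2.31
- Share of women, work disabled = 0.327/(0.327 + 0.174) = 0.653
- Share of women, others = 0.673/(0.673 + 0.826) = 0.449
- Gap = 0.204. With 30% to 60% women it stays at 0.19 to 0.20.

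**Shift from sex alone** = gap × difference between the sexes on the score. The documents do not give the second factor.

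- Assumed 5 to 15 mm on a 100 mm VAS: 0.204 × 5 = 1.0 mm; 0.204 × 15 = 3.1 mm.
- Assumed 0.2, 0.5 or 0.8 SD: 0.04, 0.10 or 0.16 SD.

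**Set against sampling error.** SE in SD units = √(1/n₁ + 1/n₂), with 65% working (SAP 1.4).

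- 200 patients, 130 vs 70: SE 0.148; 95% half-width 1.96 × 0.148 = 0.29 SD.
- 100 patients in one indication (1:1 split assumed), 65 vs 35: SE 0.210; half-width 0.42 SD.

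The rejection rate of a two-sided 5% test (level assumed) when only the sex shift b is present is 1 − Φ(1.96 − b/SE) + Φ(−1.96 − b/SE):

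| Sex difference (assumed) | b | n = 100 | n = 200 |
|---|---|---|---|
| 0.2 SD | 0.04 SD | 5% | 6% |
| 0.5 SD | 0.10 SD | 8% | 11% |
| 0.8 SD | 0.16 SD | 12% | 20% |

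**Cost of adjusting.** Age, sex, education (4 df) and disease duration use 7 df. Adjusted half-width = t(0.975; n − 9) × SE/√(1 − R²), where R² is the share of work status that the covariates explain (assumed 5%, 10%, 20%). With 100 patients, 0.42 SD becomes 0.43, 0.44 or 0.47 SD. With 80 patients (assuming 80% of 100 remain at Month 18), 0.47 becomes 0.48, 0.49 or 0.52 SD. Any outcome variance that the covariates explain would narrow these.

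**The case against.** The strongest reply is that the plan answers the question asked. The objective is a relationship, the Protocol calls the study descriptive, and it plans only to compare employed with not employed patients. A crude contrast is a legitimate answer to that. This stands, provided the result is labelled unadjusted. It does not settle the matter, because the SAP adds hypothesis tests, speaks of an effect of work status, and already controls for indication where it can, so it accepts that patient mix matters.

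The evidence for sex is indirect, and that also stands. The two percentages come from Norwegian PsA patients on conventional or biologic DMARDs and describe work disability, not WPAI question 1. The documents give no sex-specific figure for AS, and none linking sex to any score.

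Some protection exists. The 18 to 50 age limit reduces confounding by age and retirement. SAP 3.3 tabulates whether being a homemaker, unemployed, retired or part-time is due to the disease. That tells the reader why some patients are not working, but neither feature adjusts a comparison in 5.10.

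A reader might infer that the contrast could have the wrong sign, or that age, education and disease duration pile up on top of sex. The documents support neither. The sex-only shift is smaller than the sampling half-width in every scenario above. The direction of the other factors is unknown, and they may offset it; young students, for example, may answer No to WPAI question 1.

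**Conclusion.** The point holds as a gap in a secondary analysis. Indication is the only adjuster, it cannot enter for any single-disease score, and the covariates needed for an adjusted estimate are already collected. The Protocol's own background makes a difference in sex mix plausible.

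The size is uncertain and, from sex alone, small to moderate: about 1 to 3 mm on a 100 mm VAS, or 0.04 to 0.16 SD. This rests on an assumed link between sex and score, an assumed sex ratio, and Norwegian PsA figures standing in for a Belgian AS/PsA cohort. The joint influence of the remaining covariates cannot be computed from the documents, in size or direction. The finding does not make the planned comparison invalid as description, and it leaves the primary endpoint and sample size untouched.

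**What to change.** In SAP 5.10, keep the planned analysis of variance and label it unadjusted. At baseline, Month 18 and the last attended visit, report beside it the same model with age, sex and education added. Include indication only for the physician and patient disease-activity VAS and the pain VAS. Use one covariate set at all three time points so that they remain comparable. Give the adjusted mean difference (working minus not working) with its 95% CI.

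In SAP 1.6, derive disease duration as year of inclusion minus year of diagnosis. Add it only in a further sensitivity model: it may lie on the path from disease to work loss, and adjusting for it could remove part of the relation being studied.

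No new data are needed. The cost is SAP wording, a few model terms, intervals wider by about 0.01 to 0.06 SD under the assumptions above, and the loss of patients with a missing covariate from the adjusted model. Keeping the unadjusted result alongside makes that loss visible.

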5.11 Relation Between Work Productivity and Clinical Evaluations

For baseline, the change between baseline and Month 18, and the change between baseline and the last attended visit, Spearman rank correlation between:

- Absenteeism, presenteeism, TWPI, percentage activity impairment and
- DAS28 score, BSA, DLQI score, HAQ-DI score, BASDAI total score, HAQ-S scores (total score and scores for pain during the past week, general health, and stiffness), physician and patient assessments of disease activity, patient assessment of pain.

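### SAP 5.11: the all-patient Spearman correlations of the WPAI scores with the three VAS measures shared by AS and PsA are not controlled for indication, although the parallel analysis of variance is

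*SAP*

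**What the plan says.** SAP 1.7 sets two rules one after the other. The relation of TWPI to disease activity and clinical evaluations at baseline is to be "evaluated by means of the Spearman rank correlation coefficient", with no mention of indication. The relation of work status to the same kinds of measure is to be evaluated by "analysis of variance, controlled for indication, if applicable".

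Section 5 keeps the difference. SAP 5.10 has "Evaluation of the effect of work status (and indication) by means of analysis of variance". SAP 5.11 opens with "For baseline, the change between baseline and Month 18, and the change between baseline and the last attended visit, Spearman rank correlation between" and then lists the two sets of variables. It names no partial or stratified coefficient and no breakdown by indication.

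Among the clinical measures in 5.11, SAP 1.5 assigns DAS28, BSA, DLQI and HAQ-DI to PsA only, and BASDAI and HAQ-S (with its pain, general health and stiffness items) to AS only. The remaining three, "physician and patient assessments of disease activity, patient assessment of pain", are recorded in both.

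SAP 1.7 also has a general rule for variables recorded in both diseases: "the descriptions will be given for all patients as well as separately for each subgroup". Protocol 10.3.2 has a similar sentence, and it too plans correlations with TWPI without mentioning indication.

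**The concern.** A correlation computed across two pooled groups has two sources: the relation inside each group, and the difference between the group means. If AS and PsA patients differ in mean TWPI and also in mean VAS, the second source enters the coefficient. It raises the coefficient if the disease with the worse VAS also has the worse work score, and lowers it if the differences run in opposite directions.

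The plan itself treats such differences as possible. The first secondary objective asks whether work productivity evolves differently in AS and PsA, and 5.10 puts indication in the model for these same VAS measures. No reason is given for leaving it out of 5.11.

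At stake is how the third secondary objective, on correlations between disease activity or clinical evaluations and work productivity, can be read for the shared measures. A reader of the all-patient figure could not tell how much of it is the disease mix.

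**Working it through.** The documents state no figure for these correlations, so there is none to reproduce. The check has two parts: which coefficients are affected, and how far they could move.

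**Coefficients affected.** Three shared VAS measures × four WPAI scores × three analyses (baseline, change to Month 18, change to last attended visit) = 36 all-patient coefficients. Every other measure in 5.11 is recorded in one disease only, so its coefficients are within-disease already.

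**Numbers of patients.** From SAP 1.4, 200 × 0.65 = 130 employed patients at baseline, and 130 × 0.80 = 104 with 18-month data (the plan says about 100). These apply to absenteeism, presenteeism and TWPI. Activity impairment can be scored for patients not in work as well.

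**Size of the shift.** Assumptions, none of them from the documents: normal scores within each disease, the same within-disease correlation ρ in both, share p of one disease, and standardised AS–PsA differences d₁ and d₂ on the two variables. The pooled product-moment correlation is

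r = [ρ + p(1−p)d₁d₂] / √{[1 + p(1−p)d₁²][1 + p(1−p)d₂²]}

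The normal-theory conversion to Spearman is (6/π)·arcsin(r/2). It is approximate for a mixture, so simulated values (400,000 draws per setting) stand beside it. With ρ = 0.4 the within-disease Spearman is (6/π)·arcsin(0.2) = 0.385.

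Worked example with p = 0.5 and differences of 0.5 SD, so p(1−p)d² = 0.25 × 0.25 = 0.0625:
- Same direction: r = (0.4 + 0.0625)/1.0625 = 0.435, Spearman 0.419.
- Opposite direction: r = (0.4 − 0.0625)/1.0625 = 0.318, Spearman 0.305.

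| Difference on both variables (50:50 mix) | Direction | Formula | Simulation |
|---|---|---|---|
| 0.2 SD | same | 0.390 | 0.39 |
| 0.2 SD | opposite | 0.371 | 0.37 |
| 0.5 SD | same | 0.419 | 0.42 |
| 0.5 SD | opposite | 0.305 | 0.30 |
| 0.8 SD | same | 0.466 | 0.47 |
| 0.8 SD | opposite | 0.198 | 0.19 |

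Further simulated results:
- The partial Spearman given indication and the mean within-disease Spearman stay at 0.38 to 0.39 throughout.
- At a 30:70 mix the shifts are slightly smaller: about 0.42 or 0.32 at 0.5 SD, and 0.46 or 0.22 at 0.8 SD.
- With no within-disease relation (50:50), same-direction differences give a pooled value of 0.01 at 0.2 SD, 0.06 at 0.5 SD and 0.14 at 0.8 SD.
- If only one variable differs, by 0.5 SD, no spurious correlation appears, and 0.385 falls only to 0.37.

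**Change scores.** In two of the three analyses both variables are changes from baseline. A stable difference in level between AS and PsA cancels there. The shift then needs the two diseases to change by different amounts on both the work score and the VAS.

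**Comparison with sampling error.** The approximate 95% half-width of a Spearman coefficient near 0.385 is 1.96 × √[1.06/(n−3)] × (1 − 0.385²), which is 0.17 at n = 104 and 0.15 at n = 130. The shifts at 0.5 SD (+0.03 and −0.08) lie inside that. The opposite-direction shift at 0.8 SD (−0.19) does not.

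**The case against.** The strongest reply is that SAP 1.7 already provides the subgroup results. Its general rule gives both the all-patient and the by-subgroup description for shared variables. Protocol 10.3.2 calls the study essentially descriptive, and no test is stated for the Spearman coefficients, so they can be seen as descriptions. A reader might infer pooled-only correlations because Sections 3 and 4 announce a breakdown by indication and 5.11 does not. That inference fails. No part of Section 5 repeats the announcement, not even 5.1, although TWPI for AS and PsA separately is a named secondary endpoint. The breakdown in Section 5 must therefore come from the general rule.

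Whether that rule reaches correlations is unclear. SAP 1.7 introduces its definitions with "the following terminology is used for indicating the type of descriptive analysis to be performed" and then defines only descriptive statistics and frequency distributions. Even if it does reach them, the all-patient coefficient is still uncontrolled.

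Other points on that side stand:
- The third secondary objective does not specify a within-disease correlation. A pooled coefficient is a legitimate description of the enrolled patients; it is harder to interpret, not wrong.
- Disease activity already has within-disease coefficients through DAS28 and BASDAI, and AS pain through the HAQ-S item.
- The results of 5.10 and 5.11 would not be expected to agree numerically in any case. One compares mean scores by work status; the other ranks scores that, for three of the four WPAI measures, exist only for employed patients.

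**Conclusion.** The point holds as a minor one. For the three shared VAS measures, the all-patient coefficients in 5.11 are uncontrolled for indication, while the companion analysis in 5.10 is controlled, and the SAP gives no reason for the difference.

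The size cannot be known from the documents, which give neither the AS:PsA mix nor any AS–PsA difference. Under the assumptions above, the shift is negligible at about 0.2 SD and modest at 0.5 SD. It matters at 0.8 SD, above all if the differences run in opposite directions, and nothing in the documents indicates that they do. It needs a clear difference on both variables, and it applies mainly to the baseline analysis.

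Two stronger readings are not supported. A reader might infer that the whole third secondary objective is compromised, but most measures in 5.11 belong to one disease and are untouched. A reader might also infer false-positive findings. If a nominal 5% test were attached and there were no within-disease relation, same-direction differences would give rejection in 9 to 10% of cases at 0.5 SD and 29 to 34% at 0.8 SD (50:50 mix, n = 104 to 130). The SAP, however, states no test or threshold for these coefficients. The primary endpoint, the change in TWPI, is not affected.

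**What to change.** In SAP 5.11, for the physician global, patient global and patient pain VAS:

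- State that the all-patient coefficient is a partial Spearman controlled for indication, in line with 5.10.
- Confirm that the rule in SAP 1.7 on all patients and each subgroup also applies to the correlations, so that AS and PsA coefficients are reported separately.

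Indication is already recorded, so no new data are needed. The cost is a line or two of SAP text, one option in the correlation procedure and a longer table: 36 × 2 = 72 within-indication coefficients, unless the rule in 1.7 already implies them. Those rest on smaller numbers and will be less precise. The partial coefficient uses all patients and largely avoids that loss.
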